RCTC Rheumatology Common Toxicity Criteria

SAEs serious adverse events
SAP statistical analysis plan
SD standard deviation
SE standard error

SMQ standard MedDRA query
SOC system organ class
SpO2 supplemental oxygen
SRT safety review team
SSc systemic sclerosis

TEAE treatment-emergent adverse event

TLFs tables, listings, and figures

TOEP Toeplitz

TOEPH heterogeneous Toeplitz
TOR titrated oxygen requirement

ULN upper limit of normal WHO World Health Organization

1. INTRODUCTION

This statistical analysis plan (SAP) describes the statistical analysis methods and data presentations to be used in tables, listings, and figures (TLFs) in the clinical study report (CSR) for Trial HZNP-HZN-825-303. This SAP is based on the trial protocol Version 4.0 dated 01 December 2022.

1.1. Trial Objectives

The trial will be conducted in 2 parts, Part 1 (Core Phase) followed by Part 2 (Extension Phase). The Core Phase will include a 52-week, randomized, double-blind, placebo-controlled treatment period and the Extension Phase will include a 52-week, open-label extension (OLE).

1.1.1. Part 1 (Core Phase)

1.1.1.1. Primary Objective

The primary objective of the Core Phase is to demonstrate the efficacy of 2 dose regimens of HZN-825 versus placebo in subjects with Idiopathic Pulmonary Fibrosis (IPF), as determined by a comparison of change in forced vital capacity (FVC)% predicted after 52 weeks of treatment.

1.1.1.2. Secondary Objectives

- 1. Evaluate the effect of 2 dose regimens of HZN-825 versus placebo on the proportion of subjects with decline in FVC % predicted ≥ 10% from Baseline after 52 weeks of treatment (key secondary objective).
- 2. Evaluate the effect of 2 dose regimens of HZN-825 versus placebo on the changes from Baseline in the 6-Minute Walk Test (6MWT) after 52 weeks of treatment.
- 3. Evaluate the effect of 2 dose regimens of HZN-825 versus placebo on the King's Brief Interstitial Lung Disease Questionnaire (K-BILD) after 52 weeks of treatment.
- 4. Evaluate the effect of 2 dose regimens of HZN-825 versus placebo on the Living with IPF (L-IPF) after 52 weeks of treatment.
- 5. Evaluate the effect of 2 dose regimens of HZN-825 versus placebo on the Leicester Cough Questionnaire (LCQ) after 52 weeks of treatment.
- 6. Evaluate the effect of 2 dose regimens of HZN-825 versus placebo on the rate of hospitalization due to respiratory distress up to 52 weeks of treatment.

- 7. Evaluate the effect of 2 dose regimens of HZN-825 versus placebo on the composite endpoint of progression-free survival (PFS) where progression includes decline in FVC % predicted ≥ 10% from Baseline or death over 52 weeks of treatment.
- 8. Assess safety and tolerability of HZN-825 inclusive of, but not limited to adverse events (AEs), serious adverse events (SAEs) and adverse event of special interest (AESI).
- 9. Evaluate the pharmacokinetics (PK) of HZN-825.

1.1.1.3. Exploratory Objectives

6. Evaluate the effect of 2 dose regimens of HZN-825 versus placebo on mortality due to respiratory deterioration up to 52 weeks of treatment.

1.1.2. Part 2 (Extension Phase)

The overall objective of the Extension Phase is to investigate the long-term efficacy, safety and tolerability of HZN-825, a selective antagonist of LPAR1, administered at a dose of 300 mg BID to subjects with IPF in a 52-week OLE following completion of the Core Phase of the trial. The dose for the Extension Phase may be modified based on the results of the Core Phase.

Two types of Baseline are defined for the Extension Phase:

- OLE Baseline, defined as the latest measurement prior to the first dose of HZN-825 in Extension Phase
- HZN-825 Baseline, defined as the latest measurement prior to the first dose of study drug (either HZN-825 or Placebo) in the Core Phase

1.1.2.1. Primary Objective

The primary efficacy objective is to assess the efficacy of HZN-825 in subjects with IPF after 52 weeks of open-label treatment.

1.1.2.2. Safety Objective

The safety objective is to examine the safety and tolerability of 52 weeks of open-label treatment with HZN-825 based on:

- TEAE assessment
- Concomitant medication use
- Vital signs
- 12-lead electrocardiogram (ECG)
- Clinical safety laboratory results

The primary safety objective is to examine the TEAEs during 52 weeks of open-label treatment with HZN-825.

1.1.2.3. Exploratory Objectives

The exploratory efficacy objective is to evaluate the efficacy of 52 weeks of open-label treatment with HZN-825 via additional efficacy measurements:

• Proportion of subjects with decline in FVC % predicted ≥10%

- 6MWT
- K-BILD
- L-IPF
- LCQ
- •
- Hospitalization due to respiratory distress
- \bullet Composite endpoint of PFS, where progression includes decline in FVC % predicted \geq 10% or death

The exploratory PK objective is to evaluate the PK of HZN-825.

1.2. Trial Design

1.2.1. Overall Trial Design and Plan

The trial will be conducted at approximately 100 trial sites in North America, Europe, South America, Africa, Asia (including Japan) and Australia. The trial comprises 2 parts. Part 1 (Core Phase) is a randomized, double-blind, placebo-controlled, repeat-dose, multicenter trial to evaluate the efficacy, safety and tolerability of HZN-825 in subjects with IPF. Part 2 (Extension Phase) is an optional, open-label, repeat-dose, multicenter extension of the Core Phase.

At the interim analysis, the IDMC will provide recommendation to select Horizon personnel not involved in the oversight of the trial to facilitate trial continuation and dose selection for future trials. To support decisions on future dose selection and future trial design, a Horizon unblinded team may be established and receive unblinded data and perform ad hoc analyses, as needed. All unblinded data and analysis results made available to the Horizon unblinded team will be archived to allow for any potential post hoc assessments of bias. For additional details, please refer to the IDMC charter and Blinding Maintenance Plan for this trial.

An overview of the Core Phase trial design is presented in Figure 1.

Version 2.0

Figure 1. Schematic of Trial Design – Core Phase

BID=twice daily; QD=once daily

- 1. Subjects will be randomized in a 1:1:1 ratio to receive HZN-825 300 mg QD, HZN-825 300 mg BID or placebo.
- 2. If a subject prematurely discontinues trial drug, he/she will be asked to remain in the trial, participating in the scheduled trial visits through Week 52. If a subject prematurely discontinues trial drug and does not wish to continue in the trial, he/she will be asked to return for a clinic visit and undergo the Week 52 assessments. Subjects not entering the 52-week Extension Phase will return to the clinic 4 weeks after the last dose of trial drug for a Safety Follow-up Visit.
- 3. Visit windows are ±3 days for Week 4, ±7 days for Week 10 to Week 52, inclusive, and ±14 days for the Safety Follow-up Visit.
- 4. Visits at Weeks 2 and 6 are remote (telephone) visits with a ± 3 -day window.
- 5. Subjects who complete the Double-blind Treatment Period (Week 52) may be eligible to enter a 52-week Extension Phase of the trial.

1.2.3. Design of the Extension Phase of the Trial

[figure not shown]
The Extension Phase of the trial is an optional, open-label, repeat-dose, multicenter extension of the Core Phase. Subjects who complete the Double-blind Treatment Period (Week 52) in the Core Phase of the trial may be eligible to enter this 52-week Extension Phase. Subjects entering the Extension Phase will complete the Week 52 Visit, which will be considered Day 1 of the Extension Phase and will receive their first dose of open-label HZN-825 in the Extension Phase at the clinic and return to the clinic for trial visits at Weeks 56, 62 and 68, then every 12 weeks through Week 104. The Week 52 Visit activities will serve as Baseline for the Extension Phase. Subjects will return to the clinic for a Safety Follow-up Visit 4 weeks after the last dose of HZN-825.

If a subject prematurely discontinues HZN-825, he/she will be asked to remain in the trial, participating in the scheduled trial visits through Week 104. If a subject prematurely discontinues HZN-825 and does not wish to continue in the trial, he/she will be asked to return for a clinic visit and undergo the Week 104 assessments.

An overview of the Core Phase trial design is presented in Figure 2.

Version 2.0

Figure 2. Schematic of Trial Design – Extension Phase

BID=twice daily

- 1. The HZN-825 dose may be modified based on the results of the Core Phase.
- 2. If a subject prematurely discontinues open-label HZN-825, he/she will be asked to remain in the trial, participating in the scheduled trial visits through Week 104. If a subject prematurely discontinues open-label HZN-825 and does not wish to continue in the trial, he/she will be asked to return for a clinic visit and undergo the Week 104 assessments.
- 3. Visit windows are ±5 days for Week 56, ±7 days for Week 62 to Week 104, inclusive, and ±14 days for the Safety Follow-up Visit.
- 4. Visits at Weeks 74, 86 and 98 are remote (telephone) visits with a \pm 7-day window.

1.3. Sample Size and Power

Approximately 135 subjects (45 subjects per treatment group) will be enrolled in the trial. Based on a prior trial of pirfenidone [Nathan et al., 2019] in a similar subject population, change in FVC % predicted is expected to have a standard deviation of 6% to 9% after 52 weeks of treatment. Assuming a clinically important difference between HZN-825 and placebo is 3% and a common standard deviation is 9%, a sample size of 45 subjects per treatment group in the Core Phase will provide 85% probability to detect a positive signal (FVC % predicted difference for each dose vs. placebo at Week 52 >1%) and 70% probability to detect a positive signal (FVC % predicted difference for each dose vs. placebo at Week 52 >2%). If the true FVC % predicted difference for each dose versus placebo at Week 52 is 0%, then there is only 15% probability to detect a positive signal (FVC % predicted difference for each dose vs. placebo at Week 52 is 0%, then there is only 15% probability to detect a positive signal (FVC % predicted difference for each dose vs. placebo at Week 52 >2%).

The sample size for the Extension Phase is based on the number of subjects who complete the Core Phase.

[figure not shown]
Version 2.0

2. TYPE OF PLANNED ANALYSIS

2.1. Interim Analysis

An external multidisciplinary IDMC will review the progress of the trial and perform interim reviews of the study data in order to protect subject welfare and preserve trial integrity. The IDMC will include at least 1 statistician and at least 2 clinicians experienced in clinical trials and the therapeutic area. IDMC review will be conducted according to the timelines outlined in the IDMC charter.

A futility analysis for dose selection will be conducted at the interim analysis

The IDMC will recommend stopping the study for a conclusion of futility if the conditional power for both doses is less than 10% The IDMC may recommend stopping only one posology only if there is a clear safety signal that precludes continuation of one posology. Unless this occurs, the IDMC will either recommend continuing both posologies or stopping both posologies in this study.

If the IDMC recommends continuing the study, the IDMC will further recommend which of the two posologies will be used for investigation in future trials of HZN-825. The IDMC members will use the following decision criteria in making this recommendation:

- If one of the two posologies has a clear safety signal that precludes further study, the other posology will be recommended.
- If only one of the two posologies has a conditional power of at least 10% without additional safety signals then that posology will be recommended.
- 3 Similarly, if one of the two posologies has a conditional power that exceeds that of the other posology by at least 10 percentage points, without additional safety signals, the posology with the higher conditional power will be recommended.
- 4 If both posologies have similar conditional power and no unique safety signals appear with either posology, the IDMC is expected to recommend the lower dose.

To support the dose selection, and as part of the Week 28 unblinded interim analysis the FVC % predicted change from Baseline at Week 28 may be evaluated in full analysis set (FAS) subjects with concomitant treatment of standard of care at the baseline. The positive signal in the FVC % predicted change from Baseline at Week 28 and related results in subjects with standard of care will support the dose selection and future trial design.

An executive representative from Horizon will receive the recommendation from the IDMC chair. This Horizon executive representative is a senior management representative who does not have day to day responsibilities in the study and who does not have direct communication with study site personnel or study subjects.

The IDMC chair will present any data necessary to support the decision, including necessary unblinded data. All unblinded data presented to the Horizon representative will be archived to demonstrate the amount of unblinded data presented to the Horizon for post hoc assessments of bias.

A Horizon unblinded team will be established at the interim analysis. This team will receive unblinded data and perform ad hoc analyses to support decisions on dose selection, future trial design, and preparation for the potential meeting and/or requests from regulatory authorities. This team may include clinical, biostatistical, regulatory and other function representatives as needed. The unblinded information will be restricted from Horizon trial team members who are involved in any aspect of trial conduct and management. The unblinded team members will not participate in remaining trial conduct until the final unblinding of the trial has occurred following the Core Phase completion. All unblinded data and analyses results made available to the unblinded team will be archived to enable for a potential post hoc assessments of bias. Additional details of the procedural handling of the interim analysis are described in the Blinding Maintenance Plan.

The IDMC's role and responsibilities and the scope of analysis to be provided to the IDMC are provided in a mutually agreed upon charter, which defines the IDMC membership, meeting logistics, and meeting frequency.

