# 9.6.1.8 Interim Analysis

An interim analysis of the primary efficacy endpoint will be conducted using unblinded data after

This analysis will have 2 potential outcomes:

- If neither dose regimen of fipaxalparant (HZN-825) shows better efficacy compared to placebo with an acceptable safety profile, the trial will be discontinued for futility.
- If 1 or both dose regimens of fipaxalparant (HZN-825) show better efficacy compared to placebo with an acceptable safety profile, the trial will continue with no changes.

Fipaxalparant (HZN-825)

Version 5.0, Amendment 4

Protocol: HZNP-HZN-825-303

Fipaxalparant (HZN-825) Protocol: HZNP-HZN-825-303 Version 5.0, Amendment 4

The futility analysis will not be used to make a positive determination of efficacy to stop the trial.

Conditional power will be used to determine which of the options is chosen, with a conditional power of  $\geq 10\%$  required for at least 1 dose regimen to continue the trial. Other statistics, such as Bayesian statistics, may also be used for the futility analysis and dose selection.

To support the dose selection and as part of the Week 28 unblinded interim analysis, the FVC % predicted change from Baseline at Week 28 will be evaluated in subjects who were randomized with concomitant standard-of-care treatment at Baseline. Approximately 60 subjects in the standard-of-care stratum with 28 weeks of data (approximately 20 subjects per arm) will be included. The positive signal in the FVC % predicted change from Baseline at Week 28 and related results in standard-of-care subjects will support the dose selection and future trial design.

Additionally, safety will be assessed, and an fipaxalparant (HZN-825) dose regimen that has an unacceptable safety profile will be discontinued and subjects assigned to that dose regimen would be assigned to the other dose regimen for the remainder of the trial, if the other dose regimen continues.

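### SAP 2.1 counts a dose ruled out for safety in its futility test, and dose criterion 1 has no conditional-power condition, so a dose below the plan's 10% threshold can be recommended for future trials

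*SAP*

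**What the plan says.** SAP 2.1 (Interim Analysis) gives the stopping rule at study level: "The IDMC will recommend stopping the study for a conclusion of futility if the conditional power for both doses is less than 10" per cent. Dropping a single dose is a separate matter: "The IDMC may recommend stopping only one posology only if there is a clear safety signal that precludes continuation of one posology". Without such a signal, both doses continue or both stop.

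If the IDMC recommends continuing, four criteria choose the dose for future trials. Criterion 1: "If one of the two posologies has a clear safety signal that precludes further study, the other posology will be recommended". Criterion 2: "If only one of the two posologies has a conditional power of at least 10% without additional safety signals then that posology will be recommended". Criterion 3 favours the dose whose conditional power is higher by at least 10 percentage points, again without additional safety signals. Criterion 4 expects the lower dose when conditional power is similar and neither dose has a unique safety signal.

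Protocol 9.6.1.8 (and the synopsis) words the outcome differently: "If neither dose regimen of fipaxalparant (HZN-825) shows better efficacy compared to placebo with an acceptable safety profile, the trial will be discontinued for futility". A little later it says that conditional power decides between the outcomes, with 10% or more "required for at least 1 dose regimen to continue the trial". On a regimen with an unacceptable safety profile, it says that subjects assigned to it "would be assigned to the other dose regimen for the remainder of the trial, if the other dose regimen" continues.

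**The concern.** The 10% rule is meant to prevent continuing, or carrying forward, a regimen with little prospect of success. A regimen that has been ruled out for safety cannot supply that prospect, yet in SAP 2.1 its conditional power alone is enough to keep the futility stop from being triggered. Criterion 1 then applies, and it is the only one of the four criteria that does not look at conditional power. The per-dose 10% check is therefore absent in the branch where the surviving dose may fail it.

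Two things are at stake: whether the trial stops, and which dose goes into the next trial. The IDMC would be applying the rule just when safety and futility interact, which is when it most needs an unambiguous text.

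**Working it through.** **Plan's own figures first.** SAP 1.3 gives 45 per group, a difference of 3 and an SD of 9. SE = 9 × √(2/45) = 1.897. P(observed difference > c) = 1 − Φ((c − δ)/SE):
- δ = 3, c = 1: 85.4% (plan: 85%)
- δ = 3, c = 2: 70.1% (plan: 70%)
- δ = 0, c = 2: 14.6% (plan: 15%)

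All three reproduce, so the same SE is used below.

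**Conditional power (CP) at the interim.** SAP 2.1.1 gives t = 0.5, α = 0.10 (z = 1.645) and β = 0.150 (z = 1.036). CP = 10% corresponds to a normal quantile of −1.282. Solving for Z_t:
- Current trend as printed, Z_t/√t − 1.645: Z_t = √0.5 × (−1.282 + 1.645) = 0.257
- Current trend with a √(1−t) divisor, which the printed formula lacks and the hypothesised-trend formula has: Z_t = √0.5 × (−1.282 × √0.5 + 1.645) = 0.522
- Hypothesised trend: Z_t = (−1.282 × √0.5 + 1.645 − 0.5 × 2.681)/√0.5 = −0.851

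The visible text does not say to which of the SAP's two versions the 10% applies, so all three thresholds are carried.

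**Worked case, current trend as printed.** Dose A has Z_t = 1.0: 1.0/√0.5 − 1.645 = −0.231, CP 40.9%. It is ruled out for safety. Dose B has Z_t = 0, no difference from placebo: CP = Φ(−1.645) = 5.0%.
- Are both below 10%? No, so the futility stop is not triggered.
- A may be stopped for safety. Nothing in SAP 2.1 stops B alone for low CP.
- Criterion 1 recommends B. Criterion 2 cannot block this: the only dose at 10% or more is A, which has the safety signal. Criteria 3 and 4 do not apply, because each requires the absence of additional or unique safety signals.

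The hypothesised trend gives the same outcome with A at Z_t = 0 (CP 33.4%) and B at Z_t = −1.0 (CP 7.6%).

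**How often.** Assumptions: t = 0.5; BID is the dose stopped, with a true effect of 3; the safety stop is independent of efficacy; the two Z statistics are bivariate normal with correlation 0.5, which follows from the shared placebo arm and equal allocation. Interim SE at SD 9 = 1.897/√0.5 = 2.68. The quantity is P(QD < 10% and BID ≥ 10%)/P(BID ≥ 10%). For example, with QD effect 0 and the printed current trend, 43.4%/80.5% = 54%.

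| SD 9, true QD effect | Current trend, printed | Current trend, with divisor | Hypothesised trend |
|---|---|---|---|
| 3 | 14% | 19% | 2% |
| 1.5 | 31% | 39% | 7% |
| 0 | 54% | 62% | 19% |

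At SD 6, the lower end of the plan's range, the values run from 0.5% (QD effect 3, hypothesised trend) to 67% (QD effect 0, with divisor). The logic is the same with the doses reversed.

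**The case against.** The strongest reply is that three heavier readings, each of which a reader might infer, are not supported. That reply largely stands.

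- **That protocol and SAP give opposite decisions.** The protocol's outcome bullet ties efficacy and acceptable safety to the same regimen and would stop the trial here. But its conditional-power sentence asks only for one regimen at 10% or more and does not say that this must be a regimen able to continue. That is the same gap as in the SAP. The protocol is ambiguous within itself; it does not clearly contradict the SAP.
- **That subjects would be moved to a futile dose.** Reassignment appears only in the protocol, and only if the other regimen continues. SAP 2.1 has no reassignment. Joining the SAP's continuation to the protocol's reassignment builds a consequence that neither document states.
- **That the plan itself calls the remaining dose futile.** The SAP defines futility for the study. Without a safety stop, a dose below 10% continues by design whenever the other reaches 10%. The per-dose 10% appears only in criterion 2, for the choice of a future dose.

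It is also fair that an untriggered futility stop is not an order to continue. The IDMC only recommends, criterion 1 applies only if it recommends continuing, and the protocol allows other statistics to be used. The charter is not available, and text may be missing after the 10% in the stopping sentence.

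What the reply does not remove is criterion 1. It is complete as printed, has no conditional-power condition, and no other criterion supplies one.

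**Conclusion.** The point holds as a defect in SAP 2.1: the rule as written gives a wrong result in a foreseeable case. If the dose ruled out for safety has conditional power of 10% or more and the other is below 10%, the futility stop is not triggered. If the IDMC then recommends continuing, criterion 1 recommends a dose below the plan's own threshold. If both doses are below 10%, the study stops and the gap does not arise.

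The overall chance cannot be given, because the documents state no probability for a safety stop. The range of 0.5% to 67% is conditional on BID reaching 10% and then being stopped for safety independently of efficacy. It moves mainly with the assumed QD effect and the formula. The upper end uses the divisor that the SAP does not print; with the formulas as printed the maximum over the same cases is 58% (SD 6, QD effect 0, current trend).

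The change should be made: the scenario is conditional, but the repair is small and has no real downside.

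**What to change.** In SAP 2.1, evaluate the 10% criterion only among regimens still able to continue, and stop for futility if none of them reaches it. This follows the protocol's joint wording. Add to criterion 1 that the other posology is recommended provided its conditional power is at least 10%, and that otherwise no posology is recommended. Reconcile the outcome bullet and the conditional-power sentence in protocol 9.6.1.8 and the synopsis so that they say the same thing, and check that the IDMC charter agrees.

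The safety judgement, and the handling of subjects on a stopped regimen, stay with the IDMC and the sponsor; nothing here sets a dose or a safety threshold.

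Cost: two sentences in the SAP, matching wording in the protocol and a check of the charter. No extra data or analysis is needed.
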